### 3.3.4 Visual changes

Episodes of visual changes have been observed in subjects receiving trametinib. The causal relationship between a change in vision and the study treatment should be carefully explored and an ophthalmologist should be consulted. Special attention should be given to retinal (e.g., CSR) or retinal vein abnormalities (e.g., RVO).

**TABLE 7 MANAGEMENT AND DOSE MODIFICATION GUIDELINES FOR VISUAL CHANGES**

CTCAE Grade a	Adverse Event Management	Action and Dose Modification
Grade 1	
 
• Consult ophthalmologist within 7 days of onset
 
• Exclude CSR or RVO
 
• Consult retinal specialist if available in case of CSR or RVO
 
• Continue follow up examination(s) (by retinal specialist if available) for CSR and RVO
 
	
 
• Continue trametinib at the same dose level until ophthalmologic examination can be conductedb
 
• If ophthalmologic examination cannot be performed within 7 days of onset, interrupt trametinib until CSR and RVO can be excluded and symptoms resolve
 
• If CSR and RVO excluded restart trametinib at same dose level
 
• CSR: Interrupt trametinib until symptoms resolve and exam (by retinal specialist if available) shows resolution; report as SAE
 
• If CSR resolves restart with trametinib reduced by one dose level
 
• RVO: Permanently discontinue trametinib and report as SAE
 

Grade 2 and Grade 3	
 
• Consult ophthalmologist immediately
 
• Exclude CSR and RVO
 
• Consult retinal specialist if available in case of RVO or CSR for follow-up exam
 
• Continue follow up examination(s) (by retinal specialist if available) for CSR and RVO
 
	
 
• Interrupt trametinib until signs and symptoms have resolved to baseline
 
• If CSR and RVO excluded and symptoms resolved to baseline restart trametinib reduced by one dose level
 
• CSR: Interrupt trametinib until symptoms resolve and exam (by retinal specialist if available) shows resolution; report as SAE
 
• If CSR resolves restart trametinib reduced by one dose level
 
• RVO: Permanently discontinue study treatments and report as SAE
 

Grade 4	
 
Consult ophthalmologist immediately
 
Exclude CSR and RVO
 
Continue follow up examination(s) (by retinal specialist if available) for CSR and RVO
 
	
 
Permanently discontinue trametinib
 
If CSR or RVO then report as SAE
 

---------	--	--

Abbreviations: CSR = central serous retinopathy; CTCAE = Common Terminology Criteria for Adverse Events; RVO = retinal vein occlusion; SAE = serious adverse event

CTCAE Grade a	Adverse Event Management	Action and Dose Modification
a.	
Refers to CTCAE Version 5.0 'Eye disorders – Other, specify'
 
If visual changes are clearly unrelated to study treatment (e.g., allergic conjunctivitis), monitor closely but ophthalmic examination is not required.
	

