### 3.3.2 Dose Modification

#### ***Dose Modification of Dabrafenib and Trametinib and Spartalizumab for General Toxicities Related to Study Drug(s)***

In the event of a clinically significant grade 3 or 4 hematologic or non-hematologic AE, treatment may be withheld and supportive therapy administered as clinically indicated. If the toxicity or event resolves to baseline or Grade 1 in less than or equal to 21 days of stopping therapy, treatment may be restarted. Dose reduction should be considered as clinically indicated at the discretion of the treating oncologist. Any dose adjustment or interruption will be recorded.

If the toxicity does not resolve to at least Grade 1 in less than or equal to 21 days, withdrawal from the trial is recommended. However, if the investigator agrees that further treatment will benefit the subject, treatment can continue with a reduction of one or both study drugs.

Suggested dose reduction of each drug is as follows in Table 4. These dose reductions of dabrafenib and trametinib do not need to be made concurrently and will be up to the discretion of the treating investigator.

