**Table 4 Dose Levels**

Drug	Starting Dose	Dose level -1	Dose level -2	Dose level -3
Dabrafenib	150mg BID	100mg BID	75mg BID	50mg BID
Trametinib	2mg daily	1.5mg daily	1.0 mg daily	----- ---
Spartalizumab	400mg IV every 28 days	----- ---	----- ---	----- ---

If treatment related toxicities occur that are specific to combination treatment of dabrafenib and trametinib, then both treatments should be simultaneously dose reduced, interrupted or discontinued with the exceptions shown below:

Exception where dose modification is necessary for **only dabrafenib**:

- Uveitis  
Exception where dose modifications are necessary for **only trametinib**:
- Retinal vein occlusions (RVO) and retinal pigment epithelial detachment (RPED)
- Left ventricular ejection fraction (LVEF) reduction  
If a subject's dose of dabrafenib and trametinib has been reduced per the dose modification instructions, re-escalation of the subject's dose is recommended provided the following criteria are met:
  - a period of 4 weeks of treatment has passed since restarting dosing at the lower dose level and there is no recurrence of the AE
  - the subject is deriving clinical benefit

General dose modification guidelines are provided in Table 5

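### For grade 2–3 retinal vein occlusion, Table 7 permanently stops all study treatments, while Section 3.3.2 lists the event, at no stated grade, as a trametinib-only exception

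*Combined protocol and SAP*

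**What the plan says.** Section 3.3.2, in the text under Table 4, sets the general rule for toxicity specific to the dabrafenib–trametinib combination: "then both treatments should be simultaneously dose reduced, interrupted or discontinued with the exceptions shown below". One of the exception lists is headed "Exception where dose modifications are necessary for" only trametinib, and its first entry is "Retinal vein occlusions (RVO) and retinal pigment epithelial detachment (RPED". No grade is attached.

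Section 3.3.4 introduces visual changes as a trametinib matter ("Episodes of visual changes have been observed in subjects receiving trametinib") and gives the grade-by-grade instructions in Table 7:

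- Grade 1: "RVO: Permanently discontinue trametinib and report as SAE".
- Grades 2 and 3: "RVO: Permanently discontinue study treatments and report as SAE".
- Grade 4, any visual change: trametinib is permanently discontinued, with SAE reporting if the cause is central serous retinopathy (CSR) or RVO.

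Table 5, the general guideline, discontinues treatments at a first grade 4 event. No section ranks these texts against each other.

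**The concern.** The grade 2–3 RVO entry is a permanent-stop instruction, and it names more drugs than the exception in Section 3.3.2 requires. An investigator who follows the Table 7 entry ends dabrafenib for good. One who follows the Section 3.3.2 exception stops trametinib and has no instruction there to stop dabrafenib. The entry also sits oddly between its neighbours, because the rows below and above it in severity name trametinib and no other drug.

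At stake is the remaining dabrafenib for a patient with a grade 2–3 RVO and, in the adjuvant phase for a patient without pCR, the remaining spartalizumab as well. Patients without pCR who receive all three drugs are the primary-objective group.

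**Working it through.** The protocol gives no figure to reproduce. The check is a comparison of texts, with some counting.

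**Step 1. Drugs named for RVO, by source.**

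| Source | Grade | Drug(s) to stop or modify |
|---|---|---|
| Section 3.3.2, exception list | none stated | only trametinib |
| Table 7, RVO entry | 1 | trametinib |
| Table 7, RVO entry | 2–3 | study treatments |
| Table 7, whole row | 4 | trametinib |
| Table 5, general rule | 4, first occurrence | treatments |

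The Table 7 entries for grades 1 and 4 name trametinib without the word only. That word appears in Section 3.3.2.

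**Step 2. Is the grade 2–3 wording typical of Table 7?** Counting each instruction about a drug:

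- Grade 1: 6 actions, all naming trametinib.
- Grades 2–3: 5 actions, of which 4 name trametinib (for example "Interrupt trametinib until signs and symptoms have resolved to baseline") and 1 names study treatments.
- Grade 4: 1 action, naming trametinib.

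Total: 6 + 5 + 1 = 12 actions. Trametinib is named in 6 + 4 + 1 = 11. The disputed entry is the only other one.

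**Step 3. Could the plural term simply mean trametinib?** Other parts of the protocol point against that.

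- Table 9 (QTc prolongation, not a listed exception) interrupts all study treatments and, on recurrence, permanently discontinues study treatments.
- Table 8 (fall in LVEF, which is a listed trametinib-only exception) names trametinib alone. So the table for the other trametinib-only event follows Section 3.3.2, and the grade 2–3 RVO entry does not.
- Section 3.6.2 speaks of the first infusion of study treatment when it means spartalizumab, and Section 3.8.2 ties the next dose of study treatment to whether spartalizumab must stop. The term therefore covers spartalizumab for a patient on it.

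**Step 4. Drugs stopped under Table 7, read literally.**

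| Setting | Drugs being given | Grade 2–3 RVO stops | Grade 4 row names |
|---|---|---|---|
| Neoadjuvant, all patients | 2 | 2 | 1 |
| Adjuvant, pCR | 2 | 2 | 1 |
| Adjuvant, no pCR | 3 | 3 | 1 |

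Within Table 7 the less severe grades carry the wider stop in every setting. If Table 5 is applied at grade 4, the grade 4 stop widens too. Whether it applies depends on the same open question, namely whether the RVO exception governs.

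**Step 5. How much treatment is involved.** Section 3.0 gives 8 weeks before and 44 weeks after surgery. A stop at an RVO after surgery removes at most 44 weeks of dabrafenib. The ceiling is 8 + 44 = 52 weeks, which would need an RVO at the very start.

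**Step 6. How many patients.** Section 7.0 plans 45 treated patients and expects about 60% without pCR: 0.60 × 45 = 27. Section 3.2 excludes a history of RVO and predisposing factors. The documents give no RVO rate, so the expected number of cases cannot be derived from them.

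**The case against.** The strongest reply is that the specific instruction should govern the general one. The exception list sits under a heading on general toxicities, while Table 7 addresses RVO by grade, and many readers would follow the RVO row. That reading is possible. But the protocol states no precedence rule, the exception is itself specific to RVO, and the reading does not explain why grades 1 and 4 in the same table name only trametinib.

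A second reply is that Section 3.3.2 sets a minimum and Table 7 adds to it. This stands in part. Section 3.3.2 does not order dabrafenib to continue; it only does not require it to stop. A reader might infer that the protocol forbids stopping dabrafenib, or that two investigators who act differently are both fully compliant. The documents do not support either inference: continuing dabrafenib after a grade 2–3 RVO departs from the literal Table 7 entry. What can be said is that practice may differ according to which text is followed.

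A third reply is investigator discretion. Section 3.3.2 says that reductions of the two drugs "do not need to be made concurrently and will be up to the discretion of the treating investigator". That concerns dose reductions and does not settle which drugs a permanent stop covers.

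Fourth, Table 5 could produce a full stop at grade 4. This is correct. A reader might infer that the protocol as a whole gives the milder RVO the wider stop, but the documents show that only within Table 7. Table 5 does not explain the grade 2–3 entry, because it orders no permanent stop at a first grade 2 or grade 3 event.

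Finally, a full stop may be a deliberate precaution. Nothing in the documents shows which text is the slip. If the full stop is intended, the grade 4 row and the exception list need editing instead.

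**Conclusion.** The inconsistency holds as written. For grade 2–3 RVO, Table 7 permanently stops every study treatment being given, while Section 3.3.2 treats RVO at any grade as an event needing modification of trametinib only, and the rest of Table 7 agrees with Section 3.3.2. The difference concerns dabrafenib in all patients and spartalizumab in adjuvant patients without pCR. A reader might conclude that the protocol is silent on spartalizumab after RVO. At grades 2–3 it is not: the literal wording includes it.

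The point is minor. It could change what happens to an individual patient, but few of the 45 are likely to be affected given the exclusions. Any numerical chance of a case would rest on an assumed RVO rate with no anchor in the documents, so none is offered. The 24-patient sample-size argument and the primary comparison with the 50% historical rate do not depend on this rule. The conclusion rests on reading study treatments in its ordinary sense, which the usage elsewhere in the protocol supports.

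**What to change.** The clinical team should first confirm which drugs are meant to stop at each grade.

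- **If trametinib only:** give the grade 2–3 RVO entry in Table 7 the same wording as the grade 1 entry, "RVO: Permanently discontinue trametinib and report as SAE". This matches Section 3.3.2 and the other rows. One table entry changes. A sentence on whether spartalizumab continues would be useful, because the literal wording that now covers it would be gone.
- **If a full stop at grades 2–3:** name the drugs (dabrafenib, trametinib and, where given, spartalizumab), apply the same stop to grade 4 RVO, and limit the RVO exception in Section 3.3.2 to grade 1. Two table entries and one list item change.

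Either version fits in a short amendment and needs no new data, visits or patients.

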**Table 5 Dose Modification Guidelines – General**

CTCAE Grade	Action and Dose Modification
Grade 1 or Grade 2 (tolerable)	Continue study treatments at same dose level (no dose modification)
Grade 2 (Intolerable)	
1 st or 2 nd occurrence	Interrupt study treatments until toxicity resolves to $\leq$ grade 1 then restart at same dose level
3 rd or occurrence	Interrupt study treatments until toxicity resolves to $\leq$ grade 1 then restart at next lower dose level
4 th or greater occurrence	Interrupt study treatments until toxicity resolves to $\leq$ grade 1 then restart at two dose levels lower than the starting dose or discontinue treatments per investigator discretion
Grade 3	
1 st occurrence	Interrupt study treatments until toxicity resolves to $\leq$ grade 1 or baseline then restart at next lower dose level
2 nd occurrence	Interrupt study treatments until toxicity resolves to $\leq$ grade 1 or baseline then restart at two dose levels lower than the starting dose
3 rd occurrence	Discontinue treatments.
Grade 4	
1 st occurrence	Discontinue treatments

For dabrafenib and/or trametinib related adverse events: if following an interruption of dabrafenib and trametinib, an AE doesn't recover to  $\leq$  Grade 1 or baseline within 4 weeks, dabrafenib and trametinib must be discontinued.

No dose reductions are allowed for spartalizumab. Dose interruption for spartalizumab includes delaying or withholding the treatment for any reason as well as an interruption of treatment during an infusion. All dose interruptions and the reason for the dose interruption must be recorded. Dose interruption for spartalizumab includes delaying or withholding the treatment for any reason as well as an interruption of treatment during an infusion. Subjects with adverse events suspected to be related to spartalizumab including those of potential immune-mediated etiology (irAE) must be permanently discontinued from spartalizumab if (1) the AE doesn't recover to  $\leq$  Grade 1 or baseline within 12 weeks and/or (2) the dose of steroids (for the management of irAE) remains  $> 10$  mg/day prednisone or equivalent for  $> 12$  weeks. The 12 week timeframe will begin from the time the irAE reaches a grade that leads to spartalizumab interruption.

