**TABLE 8 DOSE MODIFICATION GUIDELINES AND STOPPING CRITERIA FOR LVEF DECREASE**

Clinic	LVEF-drop (%) or CTCAE grade	Action and Dose Modification
Symptomatic a	Grade 3: resting LVEF 39-20% or >20% absolute reduction from baseline	
 
Permanently discontinue trametinib.
 
Consult with cardiologist
 
Repeat ECHO after 2, 4, 8, 12, and 16 weeks or until resolution
 

	Grade 4: resting LVEF <20%	

Abbreviations: CTCAE = Common Terminology Criteria for Adverse Events; ECHO = echocardiogram; LLN = lower limit of normal; LVEF

= left ventricular ejection fraction;

- a. Symptoms may include: dyspnea, orthopnea, and other signs and symptoms of pulmonary congestion and edema.

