**TABLE 9 WITHHOLDING AND STOPPING CRITERIA FOR QTc-PROLONGATION**

QTc-Prolongation a	Action and Dose Modification
• QTcB $\geq 501$ msec	
 
• Interrupt all study treatments until QTcB prolongation resolves to grade 1 or baseline
 
• Recommend Testing serum potassium, calcium, phosphorus and magnesium. If abnormal, correct per routine clinical practice to within normal limits.
 
• Review concomitant medication usage for a prolonged QTc.
 
• Restart at current dose level
 
• If event recurs, permanently discontinue study treatments
 

Abbreviations: msec = milliseconds; QTcB = QT interval on electrocardiogram corrected using the Bazett's formula a: Based on average QTc value of triplicate ECGs. For example, if an ECG demonstrates a prolonged QT interval, obtain two or more ECGs over a brief period, and then use the averaged QTc values of the three ECGs to determine if study treatments should be interrupted or discontinued. If the QTc prolongation resolves to grade 1 or baseline, the subject may resume study treatment if the investigator agrees.

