**Table 12 Adjuvant Time and Event Table for Pathologic Non-Responders (spartalizumab, dabrafenib and trametinib)**

	Post Operat iv eh	Week 12 i	Week 16 i	Week 20 i	Week 24 i	Week 28 i	Week 32 i	Week 36 i	Week 40 i	Week 44 i	Week 48 i	Week 52 i	EOT j
Concurrent medications	X	X	X	X	X	X	X	X	X	X	X	X	X
AEs	X	X	X	X	X	X	X	X	X	X	X	X	X
PE/Vitals/ECO Ga		X	X	X	X	X	X	X	X	X	X	X	X
CBC with diff		X	X	X	X	X	X	X	X	X	X	X	X
Serum chemistry b		X	X	X	X	X	X	X	X	X	X	X	X
TSH, fT4				X			X			X			
Echocardiogram c		X			X			X			X		
12-lead EKG		X			X			X			X		X
Research Biopsy d													
If evidence of disease recurrence or metastasis													
Research Blood e		X			X			X			X		X
Research microbiome collection f		X						X					X

Disease Assessment g				X			X			X			X
Spartalizumab		X	X	X	X	X	X	X	X	X	X		
Dabrafenib and trametinib dosing	X	Continuous Daily Dosing											

- a. Includes systolic and diastolic blood pressure, pulse rate, temperature and weight.
- b. Albumin, alkaline phosphatase, total bilirubin, bicarbonate, BUN, calcium, chloride, creatinine, glucose, LDH, magnesium, phosphorus, potassium, total protein, AST, ALT, sodium.
- c. Repeat echocardiogram will be performed at month 3 and 6 and at the discretion of the investigator if there are symptoms concerning for heart failure.
- d. Should a biopsy be performed as part of standard practice, this study may request up to 4 additional cores for correlative studies.
- e. 50ml of blood will be obtained at each time point for correlative correlates.
- f. Microbiome will be collected at week 12, 36 and at recurrence. OMNIgene kits, or equivalent, will be provided
- g. PET/CT or CT of the chest, abdomen, pelvis (neck if clinically indicated) and brain MRI (or CT of the head with contrast if MRI is contraindicated).
- h. Dabrafenib and trametinib combination therapy will resume approximately two days after the patient is able to resume normal oral intake and ideally should be within 2 weeks of date of surgery. This visit could be a telephone assessment by research nurse
- i. These time points are +/- 7 days.
- j. End of treatment is defined as completion of 44 weeks of adjuvant dabrafenib/trametinib, experiencing SAE or intolerable AE mandating discontinuation of treatment or the development of progressive disease

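### Table 7 stops more than trametinib for a Grade 2–3 retinal vein occlusion, out of line with its own Grade 1 and Grade 4 rows and with Section 3.3.2

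*Combined protocol and SAP*

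**What the plan says.** Section 3.3.2 sets a default: for toxicities specific to the dabrafenib–trametinib combination, both drugs are reduced, interrupted or stopped together, apart from listed exceptions. One list is headed "Exception where dose modifications are necessary for only trametinib". Its entries are "Retinal vein occlusions (RVO) and retinal pigment epithelial detachment (RPED") and a fall in left ventricular ejection fraction.

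Table 7, in Section 3.3.4, then gives actions for visual changes by grade. For RVO they are:

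- Grade 1: "RVO: Permanently discontinue trametinib and report as SAE".
- Grades 2 and 3: "RVO: Permanently discontinue study treatments and report as SAE".
- Grade 4: trametinib is permanently stopped for any visual change at this grade, with SAE reporting if the cause is central serous retinopathy or RVO.

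Every other dose action in Table 7 names trametinib alone.

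**The concern.** Two parts of the protocol give different permanent instructions for the same event. For a Grade 2–3 RVO, an investigator working from Section 3.3.2 acts on trametinib and may keep the other drugs going. An investigator working from Table 7 also ends dabrafenib and, depending on how the cell is read, spartalizumab. Spartalizumab is the drug added in the non-pCR group, in which the primary objective is assessed.

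Within Table 7 the order is also odd: a Grade 2–3 RVO stops more drugs than a Grade 4 one. That looks more like a drafting slip in one cell than a deliberate escalation with severity.

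What is at stake is consistent dosing and the possible unneeded loss of study therapy in individual patients. No planned statistical figure depends on it.

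**Working it through.** The plan states no figure to reproduce here. The check sets the instructions side by side and counts the drugs.

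**Drugs permanently stopped for RVO**

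| Source | Grade | Neoadjuvant, or pCR adjuvant (2 drugs given) | Non-pCR adjuvant (3 drugs given) |
|---|---|---|---|
| Table 7 | 1 | 1 (trametinib) | 1 (trametinib) |
| Table 7 | 2–3 | 2 | 2 or 3, by reading |
| Table 7 | 4 | 1 (trametinib) | 1 (trametinib) |

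Section 3.3.2 requires modification of 1 drug, trametinib, and makes no distinction by grade. The number of drugs given comes from Tables 2a to 2c.

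**Excess of the Grade 2–3 cell over Section 3.3.2**

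- Neoadjuvant or pCR adjuvant: 2 − 1 = 1 drug (dabrafenib).
- Non-pCR adjuvant, if the cell means dabrafenib and trametinib only: 2 − 1 = 1 drug (dabrafenib).
- Non-pCR adjuvant, if the cell means every study drug: 3 − 1 = 2 drugs (dabrafenib and spartalizumab).

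The excess is therefore at least one drug on either reading.

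**Spartalizumab infusions at stake on the wider reading**

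Table 12, the "Adjuvant Time and Event Table for Pathologic Non-Responders (spartalizumab, dabrafenib and trametinib"), schedules infusions every 4 weeks from Week 12 to Week 48: (48 − 12)/4 + 1 = 10. An event before the Week 12 infusion forfeits all 10, and an event after the Week 48 infusion forfeits 0. An event between the Week 24 and Week 28 infusions comes after (24 − 12)/4 + 1 = 4 infusions and forfeits 10 − 4 = 6.

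**Does the general table explain the cell?**

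Table 5 does not mention RVO. For a first Grade 3 event it interrupts treatment until resolution to "grade 1 or baseline then restart at next lower dose level". It reserves discontinuation for a third Grade 3 event or a first Grade 4 event, and for a Grade 2 event allows discontinuation only as an option from the fourth intolerable occurrence. A permanent stop of several drugs for a first Grade 2 or 3 RVO does not come from Table 5.

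**Effect on the analysis**

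Section 7.0 measures relapse-free survival from surgery to recurrence or death due to melanoma. Stopping a drug is not an event, and the sample-size argument (24 non-pCR patients, 50% against 75% at 12 months) uses no dosing assumption. Power and the planned test are unchanged.

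**The case against.** *Section 3.3.2 does not forbid a stricter rule.* It says where modification is necessary, so a later event-specific table could go further. This has force: the conflict with Section 3.3.2 alone is less than absolute. But Section 3.3.2 also names RVO, no text gives Table 7 precedence, and a deliberate stricter rule would not explain why Table 7 itself returns to trametinib alone at Grade 4. The within-table pattern is the stronger evidence.

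*The drug terms are loose.* Table 9 says "Interrupt all study treatments until QTcB prolongation resolves to grade 1 or baseline", which covers every drug, whereas the Table 7 cell has no such qualifier. Section 3.3.2 also speaks of one or both study drugs under a heading that names three. This stands. A reader might infer that the cell certainly ends spartalizumab and costs 10 infusions. The documents do not settle that; the certain excess is dabrafenib.

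*Table 5 discontinues treatments at Grade 4.* This also stands. The statement that Grade 4 is treated more mildly than Grade 2–3 holds within Table 7, not across the whole protocol.

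*Table 8 might be cited as support,* since for ejection-fraction decline, another trametinib-only exception, it says "Permanently discontinue trametinib". It is weak support: the table as extracted shows only a symptomatic block and defines an abbreviation that its visible rows never use, so rows may be missing. The point does not rest on it.

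*Uveitis.* A reader might infer a second conflict: Section 3.3.2 makes uveitis a dabrafenib-only exception, and Table 7 reduces trametinib for Grade 2–3 visual changes once serous retinopathy and RVO are excluded. The documents do not support calling that an inconsistency. Table 7 does not mention uveitis, Section 3.3.4 is framed around trametinib and retinal events, and Section 3.3.2 names uveitis directly and so naturally governs.

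**Conclusion.** The Grade 2–3 RVO cell of Table 7 is wrong as written. It departs from the rows on either side of it and from the exception list in Section 3.3.2, with no stated reason and no order of precedence.

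The certain size is one extra drug, dabrafenib, permanently stopped. A second, spartalizumab, is lost in non-pCR adjuvant patients only if the cell is taken to mean every study drug, with 0 to 10 infusions forfeited according to timing.

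Severity is minor. The documents give no RVO incidence. That few of the planned 45 patients would be affected is a judgement, supported by the exclusion in Section 3.2 of patients with a history of RVO or predisposing factors. Confidence is high for the mismatch itself, which needs no outside source.

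**What to change.** Change the Grade 2–3 RVO cell to the Grade 1 wording, "RVO: Permanently discontinue trametinib and report as SAE". That brings it into line with Section 3.3.2 and with the Grade 1 and Grade 4 rows.

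If wider stopping at Grade 2–3 is intended, name the drugs to be stopped (dabrafenib, and spartalizumab or not), and align Section 3.3.2 and the other RVO rows of Table 7 so that a less severe event is not handled more strictly than Grade 4.

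The first option costs one corrected table cell in a protocol amendment, and the second a few more lines. Neither adds a procedure, because Table 7 already requires ophthalmology consultation, and neither changes the sample size or the analysis.
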